### **Randomization, Outcomes, and Masking**

Each patient will be randomly assigned, using a standard computer protocol at the General Clinical Research Center, Taipei Veterans General Hospital, Taipei, Taiwan, to intervention in a 1:1:1 ratio using sealed opaque envelopes (sequentially numbered). The study coordinator will oversee the enrollment and intervention assignment and keep allocation concealment. The Primary outcome is the change of 24 hour mean ambulatory SBP at 3 months. The secondary outcomes include the change of 24 hour mean ambulatory DBP at 3 months, decrease of left ventricular mass at 12 months, change of SBP/DBP measured by uAOBP monitoring, home BP monitoring, or central BP monitoring, change of quality of Life, change of medication count and side effects. Any possible treatment related side effects including hypotension, injurious fall, dizziness, electrolyte imbalance (serum Na <130meq/L, serum K > 5.5 or <3.0 meq/L), syncope, acute renal failure (increase in serum

creatinine > 1.5 times baseline, or increase in serum creatinine by  $\geq 0.3$  mg/dL), and bradycardia (heart rate <50 bpm detected by electrocardiogram) will be recorded and evaluated. The medication quantity will be determined by daily defined dose (DDD) calculated as per World Health Organization standard (the DDD is a system for exact quantification of drug amount and standardization to enable comparison across drug classes, eg,  $1 \times \text{DDD} = 150$  mg irbesartan or 5 mg amlodipine). The quality of life is assessed by the Bulpitt hypertension- specific questionnaire. Two-dimensional echocardiography will be obtained by Artida Echocardiograph (Toshiba Medical Systems Corporation, Tokyo, Japan) and end-diastolic left ventricular (LV) dimensions were used to calculate LV mass by an anatomically validated formula, and subsequently normalized body height The caring physicians will remain blinded to the allocation by providing them with the measured BP values through a standardized report form without the knowledge of the used BP monitoring devices. Except patient reported outcome and adverse events, the investigators and participants are blinded to all the above outcome variables (which will be calculated at the end of the study), and assessment of LV mass will be conducted on side-by-side images by a technician blinded to allocation.

### **Data Analysis and Statistical Analyses**

Based on data from our previous work, sample size (84 participants per group)

was determined on the basis of noninferiority between 3 independent groups ( $\alpha=0.05$ ;  $\beta=0.20$ ; standard deviation of ambulatory BP 11 mmHg; mean difference and non-inferior margin 5 mmHg, drop rate 10%).

We will test the normality of all parameters using the Shapiro–Wilk test. Categorical data are shown as proportions. Continuous data as means and standard deviations (SD) or as medium and interquartile ranges will be presented when appropriate.

Data will be analyzed on all patients who received the allocated strategy by intention-to-treat analysis if possible. For continuous variables of LV mass index, 24-hour ambulatory BP, heart rate, and quality of life, analysis will be undertaken using linear regression, with the dependent variable calculated as change over time. We will analyze DDD medication data recorded at all visits by using mixed regression models to account for repeated measures on individuals over time, with outcome variables log-transformed to correct heteroskedasticity where necessary.

The back-transformed means and confidence intervals are presented. Recommendations on medication use at each visit were categorized as maintain, increase, decrease or cease. A log-multinomial regression model will be used to assess the group differences for each of these 3 arms, with clustering on individuals to account for repeated measures over time.  $\chi^2$  test will be used to determine the

relationship between categorical variables. Intra-class correlations and paired t-test are used to assess the agreements between different strategies. A data safety monitoring board will be convened to oversee the progress of the study conduct and data relating to safety issue.

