## Introduction

Throughout middle and old age, blood pressure (BP) is strongly and directly related to vascular and all-cause mortality, and lowering high BP has been shown to associate with a substantial risk reduction of cardiovascular diseases. However, the traditional BP used for clinical practice, the office BP, is usually measured in a busy and hurry clinical environment, and interfered by the well-known confounding whitecoat effect. As such, unattended automated office BP monitoring (AOBP) has been proposed as an effective solution and further promoted by Canadian physicians. Nonetheless, out-of-office BP, home BP and ambulatory BP, remains the methodology of recommendation for the detection of whitecoat effect, and its prognostic value has been demonstrated to be superior to the traditional office BP. In previous systematic review and meta-analysis, home BP has been shown to be as good as ambulatory BP in predicting target organ damage and a better guiding strategy than conventional office BP. Home BP monitoring, with its ability to detect morning and masked hypertension and a better tolerability than ambulatory BP monitoring for long-term use, can therefore be considered as a strategy of choice to replace office BP monitoring for guiding hypertension management.

Moreover, BP measurements in the peripheral arteries cannot serve as direct substitutes for their central counterparts because of the long-recognized differences

of blood pressure (BP) waveforms  and values  between the central aorta and peripheral arterial system. Thus, if the decisions on medication adjustment are made solely based brachial BP, there could be a considerable risk of over- or undertreatment.

Considering that there are many better strategies for guiding hypertension management than traditional office BP, there is an apparent need for investigating their comparative effectiveness and safety in the management of hypertension. We hypothesized that home BP may be non-inferior to AOBP and central BP-guided intervention in reducing ambulatory BP and designed the present randomized controlled trial.

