## **Discussion**

### **Rationale**

The BP measurement is the clinical procedure of greatest importance given it serves as an imperative foundation in the management of hypertension, which is the most significant cardiovascular risk factor across the globe. However, a substantial whitecoat effect, the difference between office and out-of-office BP, can be observed in the measurement process of office BP in routine clinical practice, which can make the adjustment of antihypertensive agents a challenging task. Subsequently, home BP and uAOBP have been confirmed as successful strategies to eliminate the whitecoat effects. In addition, central BP has been shown to better conventional office BP in the prediction of cardiovascular risk and may be a more cost-effective strategy in the diagnosis of hypertension. In the era of evidence-based medicine, clinical trials are required to investigate the comparative effectiveness between these readily available BP monitoring strategies to inform clinical practice decisions. Using the gold standard of BP monitoring, the ambulatory BP, as the primary endpoint, we suggest home BP monitoring may be non-inferior to uAOBP and central BP monitoring as a guiding tool in the management of hypertension. Home BP is obtained by consecutive measurements and therefore is associated with a better accuracy and prognostic value than

conventional office BP. Moreover, home BP monitoring can be conducted in an easier way than uAOBP. If a comparable effectiveness could be demonstrated, it may have the potential to become the standard guiding procedure for hypertension.

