### **Double blind versus open label design for the treatment strategies**

We designed this study as a double-blind study for the clinical information will be provided for clinicians without the knowledge of the BP monitoring used for measure subjects' BP. The allocation concealment and blinding to patients, care givers, and outcome assessors will be rigorously kept avoiding possible placebo or performance bias. To our knowledge, it may be the first randomized controlled trial using the double-blind technique to evaluate the best BP monitoring strategy.

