## **Conclusion**

The GYMNs trial is ongoing now and due to complete in 2020. The trial should be fully powered to test its primary hypotheses. It is the first robust RCT to evaluate the optimal guiding strategy for hypertension will help define which BP monitoring is the most effective strategy to guide the clinical management of hypertension. Whatever the outcome, the findings of GYMNs are likely to influence future international guidelines for the choice of BP monitoring strategy in routine clinical practice in the care of hypertensive subjects.

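### The primary regression is never tied to the 5 mmHg non-inferiority margin, and the 84 per arm gives 80% power for one home BP comparison, not for the two-part hypothesis

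*Combined protocol and SAP*

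**What the plan says.** The Introduction gives the hypothesis as "home BP may be non-inferior to AOBP and central BP-guided intervention in reducing ambulatory BP". The Rationale in the Discussion repeats it: "we suggest home BP monitoring may be non-inferior to uAOBP and central BP monitoring as a guiding tool in the management of hypertension". Both name two comparators joined by 'and'.

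In Data Analysis and Statistical Analyses, the sample size of 84 per group "was determined on the basis of noninferiority between 3 independent groups". The inputs are alpha 0.05, beta 0.20, an SD of ambulatory BP of 11 mmHg, and "mean difference and non-inferior margin 5 mmHg, drop rate 10" percent. Alpha is not labelled one- or two-sided.

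For 24-hour ambulatory BP, the same section says that "analysis will be undertaken using linear regression, with the dependent variable calculated as change over time". The margin does not appear again. The only confidence intervals mentioned are the back-transformed ones that follow the medication-dose analysis.

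The Conclusion states: "The trial should be fully powered to test its primary hypotheses".

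**The concern.** A non-inferiority trial draws its conclusion from where a confidence limit falls relative to the margin. This plan has a non-inferiority hypothesis and a non-inferiority sample size. Its stated analysis does not name the contrasts, the confidence level, the comparison with 5 mmHg, or whether one or both comparators must be met.

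Two things follow.

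- Ordinary regression output invites the reading that a non-significant arm difference shows comparability. Over a range of observed results that conclusion would be wrong, and the Rationale looks to comparable effectiveness as grounds for making home BP the standard procedure.
- The power claim in the Conclusion concerns the primary hypotheses, while the sample size matches a single pairwise comparison. Requiring both comparisons to succeed has lower power than either one.

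**Working it through.** **Inputs.** From Data Analysis and Statistical Analyses: 84 per arm, alpha 0.05, power 0.80, SD 11 mmHg, margin 5 mmHg, dropout 10%. From Randomization, Outcomes, and Masking: 1:1:1 allocation, and an outcome of change in 24-hour mean ambulatory SBP at 3 months. Assumed, because the plan does not say: 11 mmHg is the SD of change, and the true difference is 0. Let d be home minus comparator in 3-month change, so that positive d is a home BP deficit.

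**Step 1: reproduce the 84.** For one pairwise non-inferiority test, n = 2(z_α + z_β)² × SD² / margin².

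- One-sided 0.025: 2 × (1.960 + 0.842)² × 11² / 5² = 75.98, so 76 evaluable. 76 × 1.1 = 83.6, so 84. (Dividing by 0.9 gives 84.4, so 85.)
- One-sided 0.05: 59.85, so 60 evaluable, or 66 to 67 with dropout. This does not give 84.

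The stated size therefore fits one comparison at one-sided 0.025 with true difference 0.

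**Step 2: the combined 5 mmHg phrase.** If the true deficit were also 5 mmHg, the distance to the margin would be 5 − 5 = 0, and power would equal alpha at any sample size. The phrase cannot be taken literally; a true difference of 0 is what reproduces 84.

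**Step 3: power at the planned numbers.** Evaluable per arm = 84 × 0.9 = 75.6. SE = 11 × √(2/75.6) = 1.789, and 5/1.789 = 2.795. Power per comparison = Φ(2.795 − z). The two contrasts share the home BP arm, so with equal arms their correlation is 0.5, and power for both is bivariate normal.

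| Alpha | Per comparison | Both |
|---|---|---|
| One-sided 0.025 | 79.8% | 68.4% |
| One-sided 0.05 | 87.5% | 79.4% |

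Simulation of 1,000,000 trials agrees at 75 and 76 per arm (68.0% and 68.8% for both at one-sided 0.025).

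**Step 4: dependence on the SD.** Solving for 80% power for both at 75.6 per arm gives an SD of change of 9.83 mmHg at one-sided 0.025, or 10.93 mmHg at one-sided 0.05.

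**Step 5: where a difference test misleads.**

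- Largest observed deficit that passes non-inferiority: 5 − 1.960 × 1.789 = 1.49 mmHg at one-sided 0.025; 5 − 1.645 × 1.789 = 2.06 mmHg at one-sided 0.05.
- A two-sided 0.05 difference test stays non-significant up to 1.960 × 1.789 = 3.51 mmHg.

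So at one-sided 0.025 an observed deficit between 1.49 and 3.51 mmHg is non-significant although non-inferiority fails; at one-sided 0.05 the range is 2.06 to 3.51. The chance of landing in it, per comparison, is:

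| True deficit (assumed) | One-sided 0.025 | One-sided 0.05 |
|---|---|---|
| 0 mmHg | 18% | 10% |
| 2 mmHg | 41% | 29% |

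**The case against.** **The regression can supply the contrasts, and 84 is correctly calculated.** Both stand. A model with arm terms yields home minus each comparator, and 84 is not an arithmetic error. What is missing is the rule that turns those estimates into a conclusion.

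**The trial is underpowered, or reaches 80% only if alpha is one-sided 0.05.** A reader might infer either, and the documents support neither. The 11 mmHg is described as the SD of ambulatory BP, not of change, and its source is a cited earlier study. If it is the SD at each time point, SD of change = 11 × √(2(1 − r)), where r is the baseline to 3-month correlation, which is not given. For assumed r of 0.4, 0.5, 0.6 and 0.7, power for both at one-sided 0.025 is about 59%, 68%, 80% and 91%. Baseline adjustment, neither stated nor excluded, would raise it further.

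**The sidedness is wide open.** The text is silent, but the stated size is informative. With a single comparison and true difference 0, one-sided 0.025 gives 84 and one-sided 0.05 gives 66 to 67. The same formula also sizes a two-sided 0.05 superiority test for 5 mmHg, but the section says noninferiority. One-sided 0.025 is the natural reading, and the sponsor need only confirm it.

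**Both comparisons need not succeed.** The Conclusion speaks of hypotheses in the plural, so two separately judged claims at about 80% each is arguable. The joint reading follows the wording in the Introduction and Rationale. If separate claims were intended, the plan should say so.

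**There is a competing superiority objective.** A reader might infer one from "to evaluate the best BP monitoring strategy" and "define which BP monitoring is the most effective strategy to guide the clinical management of hypertension". These are closing remarks on blinding and on the trial's value. Hypothesis, rationale and sizing all say non-inferiority, so these phrases need no change on this account.

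**Conclusion.** The concern holds as a gap in specification. The primary analysis is not linked to the 5 mmHg margin, to the two home BP contrasts or to a success rule. With 75.6 evaluable per arm and an SD of change of 11 mmHg, an observed deficit of about 1.5 to 3.5 mmHg could be reported as no difference when non-inferiority is not shown at one-sided 0.025.

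The 80% power belongs to one comparison. For the hypothesis as worded, power is about 68% at one-sided 0.025, or about 79% if alpha 0.05 was meant one-sided. These figures assume a true difference of 0, equal arms and an SD of change of 11 mmHg. The shortfall disappears at one-sided 0.025 if the SD of change is about 9.8 mmHg or less. The plan therefore does not yet support an unqualified claim of full power, but it does not show that the trial is too small either.

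**What to change.** Amend Data Analysis and Statistical Analyses before data are analysed by arm.

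1. Add a decision rule along these lines: *The primary analysis estimates home minus uAOBP and home minus central in the 3-month change in 24-hour mean ambulatory SBP. Non-inferiority to a comparator is concluded only if the upper limit of the two-sided 95% confidence interval is below +5 mmHg. The hypothesis is confirmed only if this holds for both comparators. A non-significant difference is not evidence of non-inferiority.* The 95% interval corresponds to one-sided 0.025, the level that reproduces 84; use a 90% interval only if the sponsor confirms that the sizing used one-sided 0.05. No alpha split is needed when both must hold.
2. Replace the combined 5 mmHg phrase with the assumed true difference (0 reproduces 84) and, separately, the 5 mmHg margin. State whether 11 mmHg is the SD of change.
3. Restate power as about 80% per comparison and about 68% for both at one-sided 0.025, conditional on an SD of change of 11 mmHg, and qualify the power statement in the Conclusion to match. If the sponsor confirms a different sidedness or SD, recalculate with it.

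The cost is wording, plus a stated power that may look less favourable. For reference, 80% for both at one-sided 0.025 with SD 11 would need 95 evaluable per arm (95 × 1.1 = 104.5, so 105 randomised, against 84). No extra patients are proposed.

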## **Method**

### **Study Design and rationale of the reference standard: invasively measured**

#### **CBP**

This is a 12-month, prospective, randomized trial. The study is scheduled to commence in June 2018. We estimate to enroll a total of 252 patients with 84 subjects allocated into 3 arms. Details of the sample size calculation is provided in the statistics section.

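### The sample-size line prints 5 mmHg as both mean difference and non-inferiority margin; 84 per arm follows from an unstated true difference of 0, and its 80% power is per comparison only

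*Combined protocol and SAP*

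**What the plan says.** Data Analysis and Statistical Analyses states that the size "was determined on the basis of noninferiority between 3 independent groups". The inputs are alpha 0.05, beta 0.20, "standard deviation of ambulatory BP 11 mmHg", and "mean difference and non-inferior margin 5 mmHg, drop rate 10" (percent). Whether alpha is one- or two-sided is not stated. No section gives an expected true difference between strategies apart from the 5 mmHg in this line.

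The Study Design section says: "We estimate to enroll a total of 252 patients with 84 subjects allocated into 3 arms". Allocation is 1:1:1 (Randomization, Outcomes, and Masking). The Introduction hypothesises that home BP guidance is non-inferior to two comparators, AOBP and central BP. The Conclusion says: "The trial should be fully powered to test its primary hypotheses".

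**The concern.** A non-inferiority sample size depends on the gap between the margin and the assumed true difference, so these are two separate inputs. The line gives one value for both. If home BP is assumed 5 mmHg worse and the margin is 5 mmHg, the gap is zero and no finite sample gives 80% power. If home BP is assumed 5 mmHg better, the gap is 10 mmHg and far fewer than 84 per arm are needed. Neither reading matches the printed size.

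At stake is how the result is read. Power here is sensitive to the assumed true difference, and that is the input the reader cannot recover from the text. If non-inferiority is not shown, a reader relying on the power claim in the Conclusion could take this as evidence against home BP, without knowing that the 80% was conditional on the strategies being equal. The same claim refers to hypotheses in the plural, while the calculation covers one comparison at a time.

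**Working it through.** **Inputs from the plan:** SD 11 mmHg, margin 5 mmHg, alpha 0.05, power 80%, dropout 10%, 84 enrolled per arm. **Assumptions not in the plan:** the sidedness of alpha and the true difference (both varied below), and that SD 11, labelled as that of ambulatory BP, applies to the 3-month change.

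**1. Reproducing 84.** Evaluable n per arm = 2 × (z for alpha + z for power)² × SD² / (margin − true difference)².

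- True difference 0, one-sided 2.5%: 2 × (1.960 + 0.842)² × 121 / 25 = 75.98, so 76. Dropout: 76 / 0.9 = 84.4, or 76 × 1.1 = 83.6. This matches 84.
- True difference 0, one-sided 5%: 60 evaluable, 66 to 67 with dropout. No match.
- One-sided 1.25% (Bonferroni for two comparisons): 93 evaluable, 103 to 104 with dropout. No match.
- Equivalence by two one-sided tests: 83 or 102 evaluable (each test at 5% or 2.5%), 92 to 114 with dropout. No match.
- Two-sided 5% superiority test of a 5 mmHg difference: again 76, because the arithmetic is identical to the first case.

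**2. The line read literally.**

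- Home BP 5 mmHg worse: margin − true difference = 5 − 5 = 0. The required n is undefined, and power equals the one-sided alpha at any n.
- Home BP 5 mmHg better: 2 × (2.802)² × 121 / 10² = 19 evaluable per arm, 21 to 22 with dropout.

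**3. Power per comparison at 76 evaluable per arm.** Standard error = 11 × √(2/76) = 1.784 mmHg. Power = Φ((5 − d)/1.784 − z), where d is the true deficit of home BP and z is 1.960 (one-sided 2.5%) or 1.645 (one-sided 5%).

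| True deficit d (mmHg) | One-sided 2.5% | One-sided 5% |
|---|---|---|
| 0 | 80% | 88% |
| 1 | 61% | 72% |
| 2 | 39% | 51% |
| 3 | 20% | 30% |
| 4 | 8% | 14% |
| 5 | 2.5% | 5% |

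**4. Both comparisons together.** The two contrasts share the home BP arm, so their estimates have correlation 0.5. Simulating one million trials with all three strategies equal, one-sided 2.5% and SD 11, the probability that both contrasts meet the margin is 68.0% with 75 evaluable per arm and 68.6% with 76.

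**The case against.** The best defence is that the line is loosely worded: mean difference may name the effect measure to which the 5 mmHg margin applies. A zero true difference is the usual planning assumption for non-inferiority. It also fits the plan's own framing, since the Study protocol and Rationale sections both speak of strategies of comparable value. Nowhere else do the documents suggest that home BP is expected to be 5 mmHg worse. Much of this stands: loose wording is the likely explanation, and the enrolment figure is sound. It does not remove the problem, because the loose reading leaves the true difference unstated and the printed line still gives a value that does not produce 84.

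A reader might infer that the trial has only 2.5% power. The documents do not support that. The figure requires both that 5 mmHg is the assumed true deficit and that the one-sided alpha is 2.5%; at one-sided 5% it would be 5%. No finite sample follows from that reading, so it cannot be how 84 was obtained.

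It would also be too strong to say that 80% power holds only at exactly zero: any true advantage for home BP gives more. If 0.05 were one-sided, 76 evaluable per arm would keep about 81% power at a deficit of 0.5 mmHg, but 84 would then not be the calculated size.

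Finally, every non-inferiority trial planned at zero difference loses power as the true deficit grows, and the plan gives no reason to expect a deficit of 1 or 2 mmHg. That is fair, and it makes a printed power curve optional.

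**Conclusion.** The point holds as a mis-stated input and an over-broad power claim. It is not an error in the number enrolled. The 84 per arm is consistent with margin 5 mmHg, SD 11 mmHg, one-sided 2.5%, true difference 0 and 10% dropout. It is not consistent with a mean difference of 5 mmHg entered beside the same margin.

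On those values the design has about 80% power for each comparison if the strategies are equal. It has less if home BP is worse, and about 68-69% for both comparisons together. The joint figure matters if the hypothesis in the Introduction is taken to require non-inferiority to both comparators; the statistical section does not say how the two are combined. The sidedness and the zero difference are inferred from the match to 84, so only the sponsor's own calculation can confirm them.

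**What to change.** After checking the sponsor's own calculation, change two places.

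- **Data Analysis and Statistical Analyses:** replace the combined 5 mmHg phrase with: assumed true difference 0 mmHg; non-inferiority margin 5 mmHg; one-sided alpha 2.5%; about 76 evaluable (84 enrolled) per arm. If the calculation used other values, state those instead.
- **Conclusion:** replace the claim of full power with: about 80% power for each comparison if the strategies are truly equal (about 68-69% to show non-inferiority to both uAOBP and central BP).

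Optionally, add the power per comparison at true deficits of 1 and 2 mmHg (61% and 39%).

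The cost is wording only. The enrolment target and design are unchanged; the stated power becomes conditional and looks less favourable.

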### **Study protocol**

Patients will be randomized to have hypertension management decisions made on the basis of the uAOBP, home BP, and central BP monitoring. Randomization will be done by using computer-generated randomization codes in 2 strata with baseline systolic BP (uAOBP) 130-155 mmHg and 155-180 mmHg. The BP measurements on left or right arm will also be determined by randomization codes.

To guide the management of hypertensive patients, medication adjustment will be made based on a published guideline with the measured BP through different BP monitoring methodologies. The use of different devices to obtain BP for guiding the care of hypertensive patients is aimed to determine whether these BP monitoring may be of comparable clinical value in routine practice. To achieve this, intervention patients will have medications titrated to normalize these different BP values. The target BP level, SBP 130 mmHg, of these different BP monitoring strategies are based on the latest guideline.

An overview of study protocol and acquired measures is presented in Table 1.

Although we encourage the adjustment of medication being adhered to the practice guideline, the choice of drug adjustment will be left to the discretion of the patient's attending doctor. During the measurement periods of home BP monitoring, no medication adjustment is allowable to preserve the comparability between different BP values. On the scheduled visits, the corresponding BP will be measured before meeting doctors and provided for clinicians to adjust patients' medication according to practice guideline. In summary, if the measured SBP is well within the target BP without possible side effects caused by antihypertensive agents, no medication adjustment is required. If the differences between measured SBP and target BP is less than 20 mmHg, the suggested maximal dose adjustment is 1 drug. If the BP differences are above 20 and 40 mmHg, addition of 2 drugs (or single pill combination) or 3 drugs (or single pill combination) are suggested, respectively. If low BP (less than 90/70mmHg) or any possible drug related side effects was noted, cautious adjustment of antihypertensive will be done. The dose adjustment and any possible side effects will be recorded throughout the whole study conduct period.

A sub-study will be performed to test the level of agreement between different measured BP values.

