#### **BP monitoring: uAOBP, central BP, and home BP**

Firstly, BP will be taken simultaneously from both upper arms by an oscillometric BP monitor (WatchBP Office Central; Microlife AG, Widnau, Switzerland). Subjects with SBP Differences between both arms more than 5 mmHg will be excluded. The performance of BP measurements will be adhered to the standard BP measurements procedures. For the uAOBP and CBP, the measurements will be conducted in a quiet room without the presence of clinical personnel. Patients will be seated in a quiet room without talking and taken as an average of 3 measurements with an automated device (HEM-907, Omron Healthcare, Lake Forest, IL) that has been preset to wait 5 minutes before measurements. Simultaneously, the central BP will be measured in the other upper arm. (WatchBP Office Central; Microlife AG, Widnau, Switzerland). The determination of the right or left upper arm for uAOBP or central BP will be made in a random order by computer generated random codes before the enrollment. As for the home BP measurements, a validated device (WatchBP Home; Microlife AG, Widnau, Switzerland) will be provided for all subjects allocated to the home BP arm to measure their BP at home. Subjects are requested to take BP in the morning (within 2 hours after awakening) and afternoon before meals for 7 consecutive days before the scheduled clinical visits. BP in the first day of the measurements will be discarded and an average of home BP (all BP reading and BP in the morning and in the afternoon) will be generated and provided

for clinicians to guide their treatment. The ambulatory BP of all subjects will be measured at baseline, at 3 months, and at the end of the study by a validated device (WatchBP O3 AFIB Ambulatory). Similarly, the choice of right or left arm for the measurement of ambulatory BP will be determined in a random manner. All the automated BP readings are stored digitally for analysis and corresponding BP values in each arm will be provided for clinicians to guide their hypertension management.

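### The primary change-score regression names no covariates, and the planning SD of 11 mmHg is not labelled as an SD of level or of change

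*Combined protocol and SAP*

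**What the plan says.** - **Outcome** (Randomization, Outcomes, and Masking): "The Primary outcome is the change of 24 hour mean ambulatory SBP at 3 months".
- **Model** (Data Analysis and Statistical Analyses), for ambulatory BP, LV mass index, heart rate and quality of life: "analysis will be undertaken using linear regression, with the dependent variable calculated as change over time". No covariate is named or excluded, there or elsewhere.
- **Baseline data** (BP monitoring section): "The ambulatory BP of all subjects will be measured at baseline, at 3 months, and at the end of the study". Table 1 places the first ABPM at Visit 1, the randomisation visit.
- **Stratification** (Study protocol): the codes are generated in "2 strata with baseline systolic BP (uAOBP) 130-155 mmHg and 155-180 mmHg". The analysis section does not mention the strata.
- **Sample size** (Data Analysis and Statistical Analyses): 84 per group, from alpha 0.05, beta 0.20, 10% drop-out, "standard deviation of ambulatory BP 11 mmHg" and "mean difference and non-inferior margin 5 mmHg". No SD of change and no correlation between baseline and 3-month values is given.

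**The concern.** There are two linked gaps.

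First, the model is open on covariates. Regressing change on arm alone satisfies the text, and so does a model that adds baseline 24-hour SBP, the stratum, or both. These give different standard errors and can give different non-inferiority conclusions from the same data. Unless the model is fixed in advance, it could be chosen after the results are seen. Read literally, the plan is a plain change-score comparison, which leaves unused a baseline value that every patient has. Leaving out the stratum as well tends to make the standard errors too large.

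Second, the outcome is a change, but the SD is worded as that of ambulatory BP. The SD of a level and the SD of a change coincide only at particular correlations. A reader therefore cannot tell which analysis the 84 per group was sized for.

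The stake is precision. Non-inferiority is judged by whether a confidence interval stays within 5 mmHg, so interval width largely decides whether a truly equivalent strategy can be shown to be so.

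**Working it through.** **Inputs from the plan:** SD 11 mmHg, margin 5 mmHg, beta 0.20, alpha 0.05 (sidedness not stated), drop-out 10%, 84 per arm.

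**Assumptions, not in the plan:** true difference 0; correlation r between baseline and 3-month 24-hour SBP from 0.3 to 0.7; 84 × 0.9 = 75.6 evaluable per arm; no multiplicity adjustment; normal approximation.

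**1. Reproduce the 84.** Evaluable n per arm = 2 × 11² × (z + 0.8416)² / 5².
- One-sided 0.025 (z = 1.960): 75.98, so 76. Allowing for drop-out, 76 × 1.1 = 83.6 or 75.98 / 0.9 = 84.4.
- One-sided 0.05 (z = 1.645): 59.85, and 59.85 / 0.9 = 66.5.

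The stated size fits one-sided 0.025, with 11 entered directly as the SD of the analysed variable.

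**2. Compare the two variances.** Let s0 and s1 be the baseline and 3-month SDs.
- Change score: s0² + s1² − 2·r·s0·s1
- Residual after baseline adjustment: s1² × (1 − r²)
- Difference: (s0 − r·s1)², which is never negative.

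Adjustment therefore cannot raise the residual variance. It costs a degree of freedom or two.

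**3. Power per comparison.** Power = Φ(5 / (SD × √(2/75.6)) − 1.96).

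*Reading A: 11 is the SD of level, equal at both times.* SD of change = 11√(2(1 − r)); adjusted SD = 11√(1 − r²).

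| r | SD of change | Power | Adjusted SD | Power |
|---|---|---|---|---|
| 0.3 | 13.02 | 66% | 10.49 | 83% |
| 0.5 | 11.00 | 80% | 9.53 | 90% |
| 0.7 | 8.52 | 95% | 7.86 | 97.5% |

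At r = 0.3 the 95% half-width, 1.96 × SD × √(2/75.6), is about 4.1 mmHg unadjusted and 3.3 mmHg adjusted.

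*Reading B: 11 is the SD of change, with equal level SDs.* Unadjusted power is 80% at every r. Adjusted SD = 11√((1 + r)/2).

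| r | Adjusted SD | Power |
|---|---|---|
| 0.3 | 8.87 | 93% |
| 0.5 | 9.53 | 90% |
| 0.7 | 10.14 | 86% |

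*Reading C: 11 is the baseline SD and the 3-month SD differs.* With s1 = 11k, SD of change = 11√(1 + k² − 2kr) and adjusted SD = 11k√(1 − r²).

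| 3-month SD | r | SD of change | Power | Adjusted SD | Power |
|---|---|---|---|---|---|
| 8.8 (k = 0.8) | 0.5 | 10.08 | 86% | 7.62 | 98% |
| 13.2 (k = 1.2) | 0.5 | 12.25 | 71% | 11.43 | 77% |
| 13.2 (k = 1.2) | 0.7 | 9.59 | 89% | 9.43 | 90% |

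**4. The same gain in patients.** At r = 0.5 with equal SDs, 80% power needs 2 × 9.53² × (1.960 + 0.8416)² / 25 ≈ 57 evaluable per arm adjusted, against 76 unadjusted.

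The further effect of the stratum, once continuous baseline 24-hour SBP is in the model, cannot be computed from the documents.

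**The case against.** The strongest reply is that nothing here is an error. A change-score regression is legitimate and unbiased under randomisation, its dependent variable matches the stated outcome, and 84 per group reproduces from the stated inputs. Omitting the stratum errs towards caution, and a wider interval makes non-inferiority harder to claim, so there is no added risk of a false claim from lost precision. All of that stands.

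The size of the gain rests on correlations and 3-month SDs that the plan does not give. It runs from large (66% against 83%) to almost nothing (89% against 90%). At r = 0.5 with equal SDs, readings A and B give identical results. This also stands, and it is why no shortfall in power can be asserted.

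The SD is attributed to the investigators' earlier work, where its meaning may be clear. That would settle the label but not the covariates, and the plan should still say which it is.

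Finally, investigators are to be blinded to most outcome variables, which are calculated at the end of the study. That limits model choice during the trial. It does not prevent choice at the final analysis, when the outcomes are available and the covariate list is still open.

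**Conclusion.** The concern holds. The primary model has no stated covariates, and nothing in the document brings baseline 24-hour SBP or the randomisation stratum into it. The level-or-change status of the 11 mmHg is also unstated; on its own that would be a labelling matter.

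Under one-sided 0.025, a true difference of 0 and 75.6 evaluable per arm, baseline adjustment raises power per comparison by about 1 to 17 percentage points across the scenarios shown. With equal SDs at the two times, adjusted power is at least 83% for r from 0.3 to 0.7 on either reading of the SD. Unadjusted power reaches the planned 80% only if 11 is the SD of change, or if it is the SD of level and r is about 0.5 or higher. If the 3-month SD is larger than the baseline SD, even the adjusted analysis can fall below 80% (77% at SD 13.2, r = 0.5).

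This is an avoidable loss of precision and a pre-specification gap. It is neither a bias nor proof of underpowering. The change should be made, but the trial's validity does not depend on it.

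**What to change.** In Data Analysis and Statistical Analyses, replace the open wording with a sentence such as: *Change in 24-hour SBP at 3 months is analysed by linear regression with arm, baseline 24-hour SBP (continuous) and randomisation stratum (unattended office SBP stratum, as randomised) as covariates; the non-inferiority confidence interval is taken from this model.* Use the matching baseline value for 24-hour DBP, LV mass index, quality of life and, where one is recorded, heart rate.

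In the sample-size sentence, state whether 11 mmHg is the SD of level, of change or of the adjusted residual; that it refers to 24-hour SBP, if it does; and the assumed r. Then confirm that 84 per group matches the chosen analysis.

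The cost is wording only. Table 1 already schedules ABPM, echocardiography and the questionnaire at Visit 1, and the stratum is known at randomisation. Heart rate has no row of its own in Table 1, so its baseline source needs confirming. The change should be made before outcome data are examined.
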